### 9.2 Subject Screening

Review of eligibility may be performed through chart review, written query or via telephone. Medical records may be requested. A screening log will be maintained indicating status.

### 9.2 Outline of Protocol Admissions and Testing

Time	Major Events	Admission Type	Length
Phase 1			
Week 1	Enrollment and consent PICC/IV line placement Liver/spleen ultrasound Obtain baseline laboratory testing Administration of 1 st and 2 nd dose	Inpatient	7 days
Weeks 2-6			
Weeks 2-6	Administration of doses 3-12 Obtain laboratory testing	Outpatient*	10 days
Week 6	Liver/Spleen ultrasound PICC line removal	Outpatient*	1 day
Week 7	Post-dose safety evaluation	Outpatient*	1 day
Phase 2			
Month 1	Initiation of open-label extension one month $\pm 7$ days month after dose 12 Obtain baseline laboratory testing Administration of dose 13	Outpatient*	1 day
Months 2-6	Administration of doses 14-18 Obtain laboratory testing	Outpatient*	1 day
Month 6	Liver/Spleen ultrasound Post-dose safety evaluation	Outpatient*	1 day

\*May be performed as inpatient if the patient remains hospitalized

### **9.3 Baseline Admissions**

Subjects who have been screened for eligibility will be admitted to the Neonatal Intensive Care Unit or the Pediatric Intensive Care Unit for baseline qualification assessments. Written informed consent will be obtained. Baseline evaluation will include the following:

1. Admission to the clinical research unit
2. Confirmation of eligibility
3. Collect vital signs including temperature, respiration,  $\text{SaO}_2$ , heart rate, and blood pressure
4. History and physical examination and neurological assessment
5. Collect blood and urine samples for clinical and research laboratory testing
7. Audiological evaluation
8. Abdominal ultrasound (liver and spleen volume)
9. Placement of a PICC line or other IV access
10. CXR

### **9.4 First Two Intravenous Drug Administrations**

Subjects will be admitted to the Neonatal Intensive Care Unit or the Pediatric Intensive Care Unit for  $7 \pm 2$  days. IV adrabetadex is provided as a 200 mg/mL solution and will be administered undiluted via PICC or other central line at a rate of 250 mg/kg/hr. A 5 kg infant receiving a 500 mg/kg dose, for example, will receive 12.5 ml of the 200 mg/ml solution. The 20% solution is isotonic with an osmolarity of  $290 \pm 30.0$  mOsm/kg and is suitable for delivery through central IV access.

Rate may be decreased in 25 mg/kg/hr increments to 175 mg/kg/hr if required. The rate and reason for reduction will be recorded. Dose will be either 500 or 1000 mg/kg.

For study participants in whom a PICC line or other central line cannot be placed, adrabetadex may be administered via peripheral IV. If administered via peripheral IV, adrabetadex will be diluted 4-fold into sterile saline prior to infusion. A 5 kg infant receiving a 500 mg/kg dose, for example, will receive 50 ml of the diluted adrabetadex (50 mg/ml solution).

Vital signs (temperature, heart rate, respiratory rate, supine blood pressure, and  $\text{SaO}_2$ ) and standard neurological checks will be conducted at least every 30 minutes during and then for the first two hours after drug administration, then every 2 hours until 6 hours post infusion, and then at least every 6 hours until 24 hours post infusion for the first two drug infusions.

Abnormal vital signs that meet criteria to be classified as adverse events according to section 11 will be reported as adverse events.

### **9.6 Doses 3-12**

These drug administrations may occur as an outpatient. Interval between dosing will be  $4 \pm 1$  days.

IV adrabetadex will be administered IV at a rate of 250 mg/kg/hr. Rate may be decreased in 25 mg/kg/hr increments to 175 mg/kg/hr if required. The rate and reason for reduction will be recorded.

Vital signs (temperature, heart rate, respiratory rate, supine blood pressure, and  $\text{SaO}_2$ ) and standard neurological checks will be conducted at least every 30 minutes during and then for the two hours after drug administration. Subject may be discharged 2 hours post administration if no issues.

### **9.7 Phase 1: Final Evaluation**

The final evaluation will occur  $2 \pm 1$  days after the 12th adrabetadex infusion. This will include a liver/spleen ultrasound. PICC line will be removed.

## **9.8 Post-dose Safety Evaluation**

Subject will be evaluated by history  $7 \pm 2$  days after the 12th adrabetadex infusion. History will be taken in person or by telephone by the study coordinator and consist of an interim medical history. The study coordinator will document the conversation and history. If discharged to home then study team will follow-up by phone on a weekly basis for two additional weeks.

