### 5.3 Study Size, Duration and Location

The study will enroll approximately 12 subjects up to a maximum of 15 subjects to account for potential study withdrawals, discontinuations or unconfirmed diagnosis of NPC. It is anticipated that this study will take four years to complete, with approximately four subjects to be enrolled per year.

Study-related assessments will be conducted at St. Louis Children's Hospital.

For each subject, the first phase of the protocol will be conducted over seven weeks; one-week inpatient followed by five weeks outpatient administrations with a post-dose safety evaluation performed one week after the final dose. The second phase of the protocol will be an open label extension conducted in an out-patient setting over six months with a post-dose safety evaluation performed one week after the final dose.

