# **6. Assessments, Procedures, and Testing**

## **6.1 Medical History and Physical/Neurological Examinations**

A medical and medication history will be obtained and a physical exam will be conducted after admission to the study center. This will ensure that the subject's medical health is adequate to participate in this study.

Subjects will be evaluated with an interim history and physical examination at least daily while admitted to the study center.

Anthropomorphic measures including weight and height will be obtained weekly in phase 1 and monthly in phase 2.

Physical and neurological examinations will be standardized.

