## **9.10 Phase 2: Post-dose Safety Evaluation**

Subject will be evaluated by history  $7 \pm 2$  days after the 18th adrabetadex infusion. History will be taken in person or by telephone by the study coordinator and consist of an interim medical history. The study coordinator will document the conversation and history. If discharged to home then study team will follow-up by phone on a weekly basis for two additional weeks.

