#### **11.6 Documentation of Adverse Events**

Subjects will be evaluated and interviewed to identify AEs during the course of the study. AEs may also be identified through clinical and neurological examinations, laboratory tests, etc. Any events occurring prior to dosing will be recorded on the Medical History CRF. Events occurring after administration of the first dose of study medication will be recorded on the AE CRF. AE that occur up to and including 30 days after administration of the last dose of study drug must be reported.

All AEs spontaneously reported by the subject or in response to a question from study personnel or revealed by observation, physical examination, or other diagnostic procedures will be recorded on the Adverse Event Form for that visit. Any clinically relevant deterioration in laboratory assessments or other clinical findings is considered

an AE and must be recorded on the AE CRF, unless otherwise stated in the protocol. AE information recorded on AE CRFs will be entered into the database on an ongoing basis.

For SAEs, a Serious Adverse Event Form must also be completed with as much information as possible and submitted in the time frame described below. When new significant information is obtained as well as when the outcome of an event is known, the Investigator should record the information on a new SAE form. If the subject was hospitalized, a copy of the discharge summary and any other relevant hospital records (e.g., admission report, laboratory test results, etc., must be included as part of the patient medical file).

All AEs considered to be related to study medication and all SAEs will be followed until resolved or until stable.

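### Adverse events are reportable through day 30 after the last dose, but for infants at home the scheduled enquiry stops at about day 19–23

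*Combined protocol and SAP*

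**What the plan says.** Section 11.6 (Documentation of Adverse Events) sets the reporting window: "AE that occur up to and including 30 days after administration of the last dose of study drug must be reported". The same section lists the sources from which events are recorded, which include "All AEs spontaneously reported by the subject or in response to a question from study personnel or revealed by observation". It also has related events and all serious events followed to resolution or stability.

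The contacts after the last dose are set elsewhere:

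- Section 9.8 (Phase 1) has the study coordinator take a history, in person or by telephone, 7±2 days after the 12th infusion. It then adds: "If discharged to home then study team will follow-up by phone on a weekly basis for two additional weeks".
- Section 9.10 (Phase 2) repeats the arrangement after the 18th infusion, again with "follow-up by phone on a weekly basis for two additional weeks" for infants who have gone home.
- Section 5.3 describes each phase as ending with a "post-dose safety evaluation performed one week after the final dose".
- The outline table in section 9.2 gives "Initiation of open-label extension one month" (±7 days) after dose 12 for infants who continue.
- Section 6.1 covers those still in hospital: "Subjects will be evaluated with an interim history and physical examination at least daily while admitted to the study center".

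Neither section 9.8 nor section 9.10 places a contact at day 30.

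**The concern.** The plan declares a 30-day window but schedules questions about only the first three weeks of it. After the second weekly call, capture moves from active enquiry to whatever a parent chooses to report, and these infants cannot report for themselves. Continued follow-up of known events does not detect new ones.

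Safety and tolerability form Aim 1 (section 4), and section 10 assesses them from descriptive summaries of adverse events. With six infants per dose level, one infant whose event goes unrecorded changes a cohort proportion by 1/6, about 17 percentage points. Phase 1 data from all of Cohort 1 also go to the DSMC before Cohort 2 opens (section 5.6). Uneven enquiry within one stated window is therefore worth removing when the remedy is a phone call.

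**Working it through.** The protocol states no last-contact day, so there is no figure to reproduce. The check is day arithmetic, counted from the last dose.

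**Inputs**

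- Day of the post-dose history, E: 7±2, so 5, 7 or 9 (sections 9.8 and 9.10).
- Calls: two, weekly, for infants at home. They have no stated windows, so I take them as exactly 7 and 14 days after the history (assumption).
- End of the reporting window: day 30 (section 11.6).

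**Last scheduled contact = E + 14; uncovered days = 30 − (E + 14)**

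| History (E) | Calls | Last contact | Uncovered days | Share of 30 days |
|---|---|---|---|---|
| Day 5 | Days 12, 19 | Day 19 | 30 − 19 = 11 | 11/30 = 37% |
| Day 7 | Days 14, 21 | Day 21 | 30 − 21 = 9 | 9/30 = 30% |
| Day 9 | Days 16, 23 | Day 23 | 30 − 23 = 7 | 7/30 = 23% |

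**Who is exposed**

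1. *Phase 1 infants at home who do not enter Phase 2.* Dose 12 is their last dose and section 9.8 is their only schedule. The 7–11 day gap applies in full.
2. *Infants who cross over.* Dose 13 comes one month ±7 days after dose 12. With a 30-day month (assumption) that is day 23–37; with 28 or 31 days it is day 21–35 or 24–38. Section 9.9 requires a check for adverse effects at each visit, so the dose 13 visit closes the interval after dose 12. Their exposure arises only after dose 18.
3. *Phase 2 completers at home.* Two readings are possible.
   - The section 9.2 outline puts the ultrasound and the safety evaluation together in Month 6, and section 5.3 puts that evaluation one week after the final dose. On this reading the 7–11 day gap stands.
   - Sections 6.3 and 6.6.1 place Phase 2 laboratory tests at baseline, 2, 4 and 6 months. If baseline is dose 13 and doses are monthly, dose 18 falls 5 months after baseline. The 6-month visit is then 6 − 5 = 1 month, about 30 days, after dose 18, and would cover the window.
4. *Infants stopped early.* Sections 9.8 and 9.10 count from the 12th and 18th infusions. An infant whose last dose was an earlier one has no contact anchored to it. Section 7.7 encourages such infants to remain on study and follows safety withdrawals until the issue settles, but it schedules no enquiry about new events at a set time after the last dose.
5. *Infants still admitted to the study center.* Daily history and examination (section 6.1) cover them while they stay. An infant still admitted at the day-7 history and sent home later is not clearly assigned the calls. If none were made, 30 − E = 21 to 25 days would follow the scheduled history, less the days spent as an inpatient.

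**The case against.** The best defence is that section 11.6 states a reporting duty, not a visit schedule. An event that a parent mentions on day 28 is still reportable, so the sections do not contradict each other in the letter. Spontaneous reports are recorded, known related events and all serious events are followed, and infants in the study center are seen daily. Crossover infants return for dose 13, and a 6-month visit may fall about 30 days after dose 18. The plan also defines no 30-day adverse-event rate that could be biased.

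Much of this stands, and it limits the point. A reader might infer that events in the last 7–11 days go unascertained; the documents support only that nobody is scheduled to ask about them. A reader might take the call condition to mean that inpatients are less well covered, but section 6.1 shows the reverse while they remain admitted. A reader might also take 23–37% as the share of events lost. It is a share of calendar days, and the documents say nothing about when events occur.

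The defence does not supply a scheduled question for Phase 1 non-continuers at home or a contact tied to the actual last dose for infants stopped early. For Phase 2 completers it depends on one of two readings of the timetable.

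**Conclusion.** The point holds as a gap between a stated reporting window and the contacts that should fill it. For infants at home, scheduled enquiry ends at about day 19–23, nominally day 21, leaving 7–11 days (nominally 9) in which new events are captured only if volunteered. It is firm for Phase 1 infants at home who do not continue. For Phase 2 completers at home it is conditional on the 6-month assessments not falling near day 30. For infants stopped early the defect is the missing anchor to the last dose received, so the 7–11 day figure does not describe them.

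The range assumes that the calls are made exactly one and two weeks after the history. The documents do not support a claim that a 30-day event rate will be biased and presented as complete: section 10 promises only descriptive summaries, and the number of events that might be missed cannot be estimated. Undercounting is the likelier direction of error, but its size is unknown. When SAE collection ends (section 11.7.1) is a separate matter and is not relied on here.

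**What to change.** In sections 9.8 and 9.10, keep both weekly calls and add one scheduled adverse-event enquiry at or just after day 30 (for example, up to 3 days later), counted from the last dose actually received. It should apply to every infant who by then has not been re-dosed and is no longer admitted to the study center, including infants stopped early. Show the contact in the section 9.2 outline. State there when the 6-month assessments fall relative to dose 18; if they fall at or just after day 30, that visit can serve as the enquiry.

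Adding a call is better than moving the second one. With calls nominally on days 14 and 30, the weekly contact would become a 30 − 14 = 16 day interval with longer parental recall.

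The cost is about one extra phone call per infant, or 15 at the maximum enrolment in section 5.3. A crossover infant whose dose 13 comes after the day-30 call could receive a second one. Dosing and clinical management are unaffected.

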## **9.9 Phase 2: Open-Label extension (Doses 13-18)**

Subjects who demonstrate significant reduction either in the glycine-conjugated trihydroxycholanic acid biomarker or serum bilirubin (direct bilirubin or direct bilirubin:total bilirubin ratio) will be allowed to crossover into the second phase of the study, an open-label phase of six months duration. In this phase of the study, dosing frequency will be monthly with IV adrabetadex for six months for a total of six administrations. Subjects will be evaluated at each study visit for evidence of adverse effects.

Entry into the open-label extension phase will occur after completion of phase 1 final evaluation. Doses 13-18 may be administered as an outpatient. In the extension phase, the subjects will continue at the same dose (mg/kg) as they received for the 12th adrabetadex infusion.

Because the adrabetadex drug will be infused through peripheral IV access for doses 13-18, the 200 mg/mL solution will be diluted 4-fold into sterile saline prior to infusion. A 5 kg infant receiving a 500 mg/kg dose, for example, will receive 50 ml of the diluted adrabetadex (50 mg/ml solution).

IV adrabetadex will be administered via peripheral IV access at a rate of 250 mg/kg/hr. Rate may be decreased in 25 mg/kg/hr increments to 175 mg/kg/hr if required. The rate and reason for reduction will be recorded.

Vital signs (temperature, heart rate, respiratory rate, supine blood pressure, and  $\text{SaO}_2$ ) and standard neurological checks will be conducted at least every 30 minutes during and then for the two hours after drug administration. Subject may be discharged 2 hours post administration if no issues.

If there is evidence of clinical deterioration during the open label phase (based on assessment by the patient's physician), dosing frequency may be increased. Increasing dosing frequency more frequently than monthly will necessitate reinsertion of a PICC line (see Section 8.8).

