This Phase 1/2a, open-label, multiple ascending dose, multi-center trial will evaluate whether Adrabetadex administered intravenously is effective in treating acute liver disease in NPC infants. The objective of this study is to determine the safety, tolerability and efficacy of intravenous adrabetadex in NPC disease. The primary endpoint is the efficacy of adrabetadex to reduce plasma levels of glycine-conjugated trihydroxycholanic acid ("bile acid biomarker"), an NPC-specific pharmacodynamic biomarker. Secondary endpoints are assessment of the dose-response relationship for attenuation of liver dysfunction, as determined by reduction in serum transaminases (ALT and AST) and liver size. Exploratory lipid, protein, and inflammatory biomarkers will also be examined. This study will enroll up to 12 subjects (6 subjects per dose level) and evaluate two dose levels (500 and 1000 mg/kg). In the first phase of the study, drug will be administered twice a week for six weeks for a total of 12 administrations. Subjects who demonstrate either a significant reduction in the glycine-conjugated trihydroxycholanic acid biomarker or serum bilirubin (direct bilirubin or direct bilirubin:total bilirubin ratio) will be allowed to crossover into a second open-label phase. In this phase of the study, drug will be administered monthly for six months for a total of six administrations. Serum transaminases (ALT and AST) and an abdominal ultrasound will be obtained at the end of the 6-month open-label extension phase. Efficacy will be assessed by reduction in serum transaminases and reduction in spleen volumes. NPC biomarkers [(cholestane-3 $\beta$ ,5 $\alpha$ ,6 $\beta$ -triol (CT), glycine-conjugated trihydroxycholanic acid (GCA), phosphocholinesterase (PPCS)/lysoSM-509 (Lipid-509), 24(S)-hydroxycholesterol (24-OHC), 27-hydroxycholesterol (27-OHC), and neurofilament light chain (nfL)] will also be obtained at these time points and will be considered exploratory outcome measures.

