### 5.4 Eligibility Criteria

#### 5.4.1 Inclusion Criteria

1. Age 0 to 6 months of age at time of enrollment, both genders, and any race/ethnicity.
2. Diagnosis of NPC (either NPC1 or NPC2) based upon meeting any of the two following conditions:
  - A. Two variants classified as pathogenic or likely pathogenic in *NPC1/NPC2* on clinical laboratory testing , or
  - B. One variant classified as pathogenic or likely pathogenic on clinical laboratory testing and a positive NPC biochemical marker (oxysterol or bile acid biomarker or PPCS/Lyo509) test, if acid sphingomyelinase deficiency and cholesterol ester storage disease have been excluded either by clinical molecular testing of the *SMPD1* and *LIPA* genes or by clinical biochemical assay for acid sphingomyelinase and lysosomal acid lipase enzymes (or a combination of enzymatic and molecular testing).
3. Subjects with evidence of NPC-related liver disease as defined by direct bilirubin (DB) >2mg/dL or DB/total bilirubin ratio >0.2.

Variants will be interpreted using the American College of Medical Genetics guidelines for the interpretation of sequence variants and testing must be performed by a CLIA-certified laboratory.

4. Ability to travel to a research site.
5. Willing to participate in all aspects of trial design including serial blood collections.
6. Parent / guardian must provide written informed consent to participate in the study. Because of the age range intended for inclusion, assent will not possible.

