### **6.6.1 Hematology/Chemistry**

Blood samples for the clinical laboratory tests will be collected by a qualified person using either the central line, by indwelling catheter, or by venipuncture.

Testing will include the following (phase 1: 2.5 mls/time point; 10 mls total over six weeks, phase 2: 2.5 mls/time point; 10 mls total over six months):

Hematology: complete blood count (CBC) with differential and platelet count, and prothrombin time (PT).

Clinical chemistry: electrolytes, glucose, blood urea nitrogen (BUN), creatinine, AST, ALT, GGT, alkaline phosphatase, bilirubin (direct and total), albumin, calcium, magnesium, phosphorus, and CK.

In phase 1, testing will occur at baseline, 2, 4 and 6 weeks. In phase 2, testing will occur at baseline, 2, 4, and 6 months. For study subjects, the amount drawn will not exceed the lesser of 50 ml or 3 ml per kg in an 8 week period and collection may not occur more frequently than 2 times per week.

Lab results do not need to be resulted and reported prior to dosing.

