## **7.7 Subject Withdrawal**

Guardians/parents will be informed that they have the right to withdraw from the study at any time for any reason without prejudice to their medical care. Subjects may be withdrawn from the study for any of the following reasons:

- Parent/guardian request
- Parent/guardian is unwilling or unable to comply with the protocol
- Medical reason, at the discretion of the Investigator or Medical Monitor
- Occurrence of the following:
  - a. any Grade 3 AE (per NCI's CTCAE) possibly or definitely related to study drug
  - b. any Grade 4 toxicity
  - c. any subject with pulmonary complications or evidence of renal injury
  - d. determination that the limit of safety and/or tolerability has been reached. In the context of adrabetadex administration, limit of tolerability is defined as a new oxygen requirement or evidence of renal injury.
  - e. evidence of development or worsening of liver synthetic function (monitored by serum albumin and PT) or evidence of development or worsening of hepatic encephalopathy (monitored by serum ammonia levels).

Although study treatment will cease, subjects will be encouraged to remain on study in order to collect all of the data prescribed in the protocol. The reasons for subject withdrawal will be recorded in the subject's CRF.

For a withdrawal due to a safety issue, subjects will be followed until the safety issue is resolved or returns to baseline level. Additionally, any appropriate referrals will be made as needed.

Any usable data from withdrawn subjects will be included in safety and efficacy evaluations. Withdrawn subjects may be replaced.

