These data from three subjects previously treated with IV adrabetadex support the utility of this plasma NPC biomarker as a potential outcome measure to monitor the effects of IV adrabetadex on peripheral tissues. Utilizing this data, we would have approximately 80% power to detect a 33% reduction in the plasma biomarker concentration in 5 subjects. Utilizing this data, we would have approximately 57, 80 and 99% power to detect a 25, 33 and 50%, respectively, reduction in plasma biomarker concentration in 5 subjects.

The secondary outcome measure for this trial is the plasma AST and ALT levels.

For group comparisons, such as comparing mean values of primary outcome measurements, the statistical significance of differences in mean values will be determined by a two-tailed single-factor ANOVA or Student's t test. To perform correlations, such as for comparison of primary/secondary outcome data with NIH severity scale values or clinical assessments, data will be analyzed using Pearson and Spearman correlations, as appropriate. A p-value of 0.05 or less was considered significant. A Bonferroni posttest correction will be used to adjust for multiple comparisons (e.g., when analyzing the panel of secondary outcome measures).

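### The direct:total bilirubin ratio can fall while both bilirubin values rise, so the Phase 2 entry rule can count an infant with rising bilirubin as a responder

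*Combined protocol and SAP*

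**What the plan says.** The entry rule has the same three alternatives in sections 1, 3, 5.6, 9.1 and 9.9: the bile acid biomarker, direct bilirubin, or the ratio of direct to total bilirubin. Section 9.9 admits "Subjects who demonstrate significant reduction either in the glycine-conjugated trihydroxycholanic acid biomarker or serum bilirubin (direct bilirubin or direct bilirubin:total bilirubin ratio". The Précis closes the same clause with "serum bilirubin (direct bilirubin or direct bilirubin:total bilirubin ratio) will be allowed to crossover into a second open-label phase". Any one alternative suffices, and no section adds a condition on direct or total bilirubin when the ratio is the one used.

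The two bilirubin measures are those used at enrolment. Section 5.4.1 takes "Subjects with evidence of NPC-related liver disease as defined by direct bilirubin (DB) >2mg/dL or DB/total bilirubin ratio >0.2".

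No section defines a significant reduction for one infant. The only significance level is in section 10, "A p-value of 0.05 or less was considered significant", in a paragraph on group comparisons and correlations.

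Direct and total bilirubin are both on the chemistry panel of section 6.6.1, where "In phase 1, testing will occur at baseline, 2, 4 and 6 weeks". That section adds that "Lab results do not need to be resulted and reported prior to dosing". The schedule table in section 9 puts dose 13 one month, plus or minus 7 days, after dose 12.

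**The concern.** A ratio can improve for the wrong reason. Direct over total falls if direct bilirubin drops, which is what a response in cholestatic disease should look like. It also falls if total climbs faster than direct. The rule treats the two alike, so an infant with higher direct and higher total bilirubin at week 6 can meet the bilirubin response criterion.

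What is at stake is the basis for continued dosing. Meeting the criterion opens six further monthly infusions in infants. Section 7.6 justifies the risk by the prospect of direct benefit, so apparent response should not rest on a number that improved because bilirubin went up.

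**Working it through.** The plan gives no figure to reproduce on this point, and the documents contain no infant bilirubin data. All bilirubin values below are therefore assumed, chosen to show what the rule allows. The rule comes from section 9.9, the 0.2 threshold from section 5.4.1, the sampling weeks from section 6.6.1 and the 0.05 level from section 10.

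**Identity.** Let D and T be baseline direct and total bilirubin, and D′ and T′ the week 6 values. The relative change in the ratio is (D′/D) ÷ (T′/T). It is below 1 whenever T rises proportionally more than D, even if D rises.

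**Both values up, under four readings of a significant reduction:**

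| Reading | Direct (mg/dL) | Total (mg/dL) | Ratio |
|---|---|---|---|
| Any fall | 3.0 → 3.1 | 5.0 → 5.5 | 0.600 → 0.564 |
| Percentage cutoff | 3.0 → 3.6 | 5.0 → 9.0 | 0.600 → 0.400 (−33%) |
| Crossing 0.2 | 3.0 → 3.6 | 12.0 → 18.5 | 0.250 → 0.195 |
| p ≤ 0.05, weeks 0, 2, 4, 6 | 3.0, 3.2, 3.4, 3.6 | 5.0, 6.2, 7.6, 9.0 | 0.600, 0.516, 0.447, 0.400 |

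In the last row the least-squares slope of the ratio is −0.0334 per week, p = 0.007, while both values rise at every sample. Applying 0.05 within one infant is an assumption.

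In the second row, indirect bilirubin goes from 5.0 − 3.0 = 2.0 to 9.0 − 3.6 = 5.4, so 3.4 of the 4.0 mg/dL rise in total is indirect. In the third row, direct bilirubin stays above 2 mg/dL, so the infant still meets the enrolment definition of liver disease.

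**How large the rise in total must be.** If direct rises by a fraction d and the ratio falls by a fraction r, total must rise by (1 + d)/(1 − r) − 1.

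| Direct up | Ratio down 25% | Ratio down 33% | Ratio down 50% |
|---|---|---|---|
| 10% | 47% | 64% | 120% |
| 25% | 67% | 87% | 150% |
| 50% | 100% | 124% | 200% |

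So a large relative fall in the ratio with direct bilirubin also up needs a substantial rise in total.

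**What a shared cutoff implies.** Suppose direct bilirubin and the ratio use the same percentage cutoff r. Passing on the ratio means D′/T′ ≤ (1 − r)D/T. Failing on direct means D′ > (1 − r)D. Together, T′ ≥ D′T/((1 − r)D) > T. Every infant who enters on the ratio but not on direct bilirubin then has a higher total. This does not show that direct rose. For example, direct 3.0 → 2.2 (−27%) with total 5.0 → 5.5 gives a ratio of 0.60 → 0.40 (−33%), and that infant's direct bilirubin improved.

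**The case against.** The case for leaving the rule alone is substantial.

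- **Total bilirubin is not ignored.** It is the denominator, so nobody can apply the ratio route without both values. Entry of a visibly worse infant would be a decision, not an oversight.
- **Crossover is permitted, not required.** The undefined term also leaves room for clinical judgement.
- **Other rules address liver worsening.** Section 7.7 allows withdrawal for "Medical reason, at the discretion of the Investigator or Medical Monitor" and lists worsening synthetic function or encephalopathy, followed by albumin, PT and ammonia. Table 1, row D, in section 7.8 withdraws an infant for any drug-related Grade 3 event. Section 11.6 opens its laboratory rule with "Any clinically relevant deterioration in laboratory assessments or other clinical findings is considered" and requires the event to be recorded as an AE.
- **The measures are coherent.** The trial treats cholestatic disease, and entry to the extension uses the same two measures as enrolment.
- **Withholding the extension is not shown to protect the infant.** Section 9.9 lets dosing frequency increase on clinical deterioration.

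All of this stands and limits the importance of the point. It does not remove it: none of these provisions sets a bilirubin condition for entry, and nothing in the text makes the investigator decline an infant whose two values both rose.

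A reader might go further and infer that the rule will send infants with worsening liver disease to more dosing, or that every ratio-only entrant is worsening. The documents support neither. In the percentage example the rise is mainly indirect bilirubin, which is possible rather than proven liver worsening. The shared-cutoff result concerns total only, and under other readings some ratio-only entrants improve on both values: direct 5 → 3.5, total 20 → 18, ratio 0.25 → 0.194.

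**Conclusion.** The point holds as a statement about the rule as written. A fall in the direct:total ratio is a stand-alone route into Phase 2, and an infant whose direct and total bilirubin both rose can meet it. That follows from the identity and does not depend on how a significant reduction is defined among the four readings tried. The particular values are assumptions.

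Frequency and harm cannot be judged from the documents. A reader might also infer that trial results are biased. They are not affected: the Phase 1 primary outcome is the bile acid biomarker, the secondary outcomes are transaminases and liver size, Phase 2 efficacy is transaminases and spleen volume, and no responder rate is defined. This is a low-priority, cheap improvement to an access rule.

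**What to change.** Add one sentence wherever the rule appears (sections 1, 3, 5.6, 9.1 and 9.9): *A fall in the direct:total bilirubin ratio counts only if direct bilirubin at week 6 is not above baseline; otherwise entry needs the biomarker route or DSMC agreement.*

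All four both-up examples are then diverted (week 6 direct of 3.1 or 3.6 against 3.0). The infants with direct 5 → 3.5 and 3.0 → 2.2 still enter on the ratio.

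A condition on total as well would be too broad. Under a shared cutoff it would send every ratio-only entrant to the DSMC, including the infant whose direct bilirubin fell 27%. The price of the narrower condition is that an infant with flat or lower direct bilirubin and a higher total still qualifies.

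The cost is one amendment sentence. Both values are already measured at baseline and week 6, about a month separates doses 12 and 13, and section 11.5 already lets the DSMC meet ad hoc. The downside is that an infant with a small chance rise in direct bilirubin must use the biomarker route or obtain DSMC agreement.
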